Figure 4. Mean startle magnitude difference between threat and safe. Anxiety-potentiated startle magnitude during View (no task) was significantly higher, and during 3-back significantly lower, than anxiety-potentiated startle at all other levels of cognitive load. Anxiety-potentiated startle during 1-back and 2-back did not differ. Anxiety-potentiated startle during all conditions was different from zero. Error bars represent the within-subjects standard error for the repeated measures general linear model (GLM) comparing startle during threat versus safe across load. *p < 0.5. The two key questions are 1) to which degrees various cognitive processes (e.g., working memory, inhibition) are affected (impaired/facilitated) by anxiety induced by shock anticipation, and 2) to which degree various cognitive tasks down-regulate experimental anxiety.

CNS IRB Protocol Template (rev. 9-21-11)

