This study will examine whether greater WM capacity or practice is associated with increased or decreased anxiety during performance of a WM task during threat of shock. On the one hand, increase in WM capacity could be associated with more ability to allocate resources to anxious thoughts, therefore increasing anxiety. On the other hand, better WM reflects better ability to screen out intrusive stimuli and thoughts, thereby decreasing anxiety. As for task practice, we hypothesize that practice will make more resources available to allocate to anxious thoughts.

Subjects will be asked to remember verbal and nonverbal stimuli. These stimuli consist of words, pictures, letters or spatial locations in series of stimuli. Participants will be instructed to remember one, two, or three stimuli back from the current stimulus on the screen (n-back task). There will be 2 groups. One group will practice the N-back task

minimally (e.g., 5 min) and the other group will have more extensive training (e.g., 20 min).

Sub-study C: Effect of anxiety on sustained attention to response task (SART)

SART are sustained attention tasks during which a button-press response is made to frequent targets and responses are withheld to rare non targets. SART have been used extensively to study inattention, "off-task thinking", task-unrelated thoughts, and 'mind wandering" (Robertson, Manly et al. 1997). An advantage of this task is that it enables us to identify periods when the mind wanders. When the mind wanders, subjects make errors of commitment (they button-press to non-targets). We will use SART to attempt to identify periods of anxious thoughts.

Subjects will have to respond to frequent targets (e.g., digits 1, 2, 3...) and to withhold response to rare non targets (e.g., 3). We will examine the association between response speed and anxiety as assessed with startle. Mind wandering in SART is associated with faster RT. We will examine whether faster RT is associated with larger potentiated startle. We will also probe subjects' thoughts (on-task, off-task, anxious thoughts) after each startle stimulus to assess whether anxious thoughts predict startle potentiation.

Sub-study D: Effect of anxiety on Stroop task

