10. STATISTICAL ANALYSIS

The accrual ceiling for this protocol is 1575 healthy controls. The overall current target N for the protocol is 148 healthy controls.

Sub-study A (previously Study 2a)36 subjectsSub-study C (previously Study 2c)34 subjectsSub-study E (previously Study 2e)48 subjectsSub-study F (previously Study 2f)30 subjects

Study 2a: Working memory and anxiety

Analysis of the data: Startle and performance data will be analyzed with ANOVAs with repeated measures using condition (threat, safe) x Load (low, high). Power analysis: Based on pilot and published works in our lab, we expect an small/moderate effect size for startle potentiation (Cohen's d=0.3). A priori calculations indicate that the testing of 30 participants at an alpha of 0.05 would provide power of 0.80 to detect a significant 2 (Condition) x 2 (Load) interaction on startle response. Assuming a 20% attrition rate, we will collect (about) 36 subjects.

Study 2c: Effect of anxiety on sustained attention to response task (SART)

Analysis of the data: The main analysis is to compare startle magnitude when subjects focus on the task and when their mind wander with ANOVAs with repeated measures using condition (threat, safe) x thought (on task, off task).

Power analysis: Based on pilot works in our lab, we expect an small/moderate effect size for startle potentiation (Cohen's d=0.4). A priori calculations indicate that the testing of 28 participants at an alpha of 0.05 would provide power of 0.80 to detect a significant 2 (Condition) x 2 (Load) interaction on startle response. Assuming a 20% attrition rate, we will collect (about) 34 subjects.

Study 2d: Effect of anxiety on Stroop task

Study is 2d is is closed for accrual. We are currently analyzing the data.

Study 2e: Pilot studies

These pilot experiments are designed to determine the parameter of stimulation of study that will be used in our neuroimaging, psychopharmacological, and clinical studies conducted in our other protocols (03-M-0093, 02-M-0321, 02-M-0263). We use tasks in 4 domains, 1) sensory processing, 2) conflict, 3) executive function, and 4) working memory. We will use 12 subjects per domain for a total of 48 subjects.

Study 2f: Pilot study of sural nerve stimulation

This pilot study investigates the location of the stimulating and recording electrodes and different types of stimulus delivery. We have requested 30 subjects.

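### SART sub-study (Study 2c): power is stated for a Load factor that the task lacks and cannot be checked from its inputs, and two stated questions have no named analysis

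*Combined protocol and SAP*

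**What the plan says.** Section 10, Study 2c, plans to compare startle between on-task and mind-wandering periods with "ANOVAs with repeated measures using condition (threat, safe) x thought (on task, off task", and calls this the main analysis. The effect-size input is "we expect an small/moderate effect size for startle potentiation (Cohen's d=0.4". The power sentence then reads "testing of 28 participants at an alpha of 0.05 would provide power of 0.80 to detect a significant 2 (Condition) x 2 (Load) interaction". With 20% attrition this becomes about 34 subjects.

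Study 2a, in the same section, does have a Load factor (low, high). Its input is "we expect an small/moderate effect size for startle potentiation (Cohen's d=0.3", and it claims that "testing of 30 participants at an alpha of 0.05 would provide power of 0.80 to detect a significant 2 (Condition) x 2 (Load) interaction".

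The Figure 4 legend in section 2, which concerns an n-back task, presents anxiety-potentiated startle as "Mean startle magnitude difference between threat and safe".

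Section 4(d), Sub-study C, describes responding to frequent targets and withholding responses to rare non-targets, with no load manipulation. It states two questions: "We will examine whether faster RT is associated with larger potentiated startle" and "We will also probe subjects' thoughts (on-task, off-task, anxious thoughts) after each startle stimulus to assess whether anxious thoughts predict startle potentiation". Section 9 makes startle and cognitive-task performance the primary outcomes.

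**The concern.** There are two separate problems.

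The first is the power statement. It names a factor that belongs to Study 2a, so no power is stated for the comparison that Study 2c calls its main analysis. The input is an effect size for startle potentiation, which in the section 2 legend is a threat-minus-safe difference. The claim is about an interaction, which is the change in that difference between thought states. The 80% is the stated basis for 34 subjects, and a reader cannot tell which effect it covers.

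The second is the analysis. Section 4 collects three probe categories and asks about reaction time (RT). Section 10 has two thought levels and no RT term. The model, the RT window and the thought coding therefore stay open until the data have been seen. The coding also affects the main comparison: off task means one thing if anxious probes are pooled into it and another if they are dropped. The RT question is the one that links the two primary outcomes in this sub-study.

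**Working it through.** **Inputs.** From section 10: Study 2c has d = 0.4, n = 28, alpha 0.05, power 0.80; Study 2a has d = 0.3, n = 30, same alpha and power. Not given: sidedness, the within-subject correlation, and how d maps to an interaction. I take tests as two-sided unless noted and treat correlations as assumptions.

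**1. The label.** A 2 x 2 within-subject interaction reduces to one contrast per subject: (threat − safe) in one state minus (threat − safe) in the other. It is tested by a one-sample t on n − 1 df with noncentrality dz·√n, where dz is the standardized contrast. This is the same whether the second factor is Load or Thought.

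**2. Trying to reproduce 28.** Enrolment follows simply: 28 × 1.2 = 33.6, or about 34. The 28 itself depends on the reading of d:

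- *Reading A, d is dz.* Noncentrality is 0.4 × √28 = 2.12, so power is 53% (66% one-sided). If all 34 gave data, power would be 62%. Reaching 80% takes 52 completers (41 one-sided). At n = 28, 80% needs dz = 0.549.
- *Reading B, d is in SDs of one potentiation score*, with correlation ρ between the two scores: dz = 0.4/√(2(1 − ρ)). Power at n = 28 is 41%, 53%, 75% and 80% at ρ = 0.3, 0.5, 0.7 and 0.735.
- *Reading C, f = d/2 = 0.2, four cells, 1 df*, with common correlation r: λ = n·4·f²/(1 − r) = 28 × 4 × 0.04/(1 − r) = 4.48/(1 − r). Power at n = 28 is 68%, 75%, 82% and 90% at r = 0.3, 0.4, 0.5 and 0.6, and 80% at r = 0.47. At r = 0.5 the smallest n for 80% is 27.

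So 28 can be reached, but only with a conversion and a correlation that the plan does not state.

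**3. Cross-check against Study 2a.** Suppose both sub-studies use one scaling, dz = k·d.

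| Scaling set by | dz for 80% | k | Implied dz in the other study | n the other needs | Power at the other's stated n |
|---|---|---|---|---|---|
| 2c (28 at d = 0.4) | 0.549 | 0.549/0.4 = 1.373 | 1.373 × 0.3 = 0.412 | 49 (stated 30) | 59% |
| 2a (30 at d = 0.3) | 0.529 | 0.529/0.3 = 1.764 | 1.764 × 0.4 = 0.706 | 18 (stated 28) | 95% |

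For both stated sizes to hold, the correlations must differ: 0.73 (2c) and 0.84 (2a) on reading B, or 0.47 and 0.68 on reading C. On reading C with r = 0.5 in both, 2c has 82% power while 2a has 61% at n = 30 and would need 46.

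**4. Questions against models.**

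| Question | Where stated | Study 2c model in section 10 |
|---|---|---|
| Startle, on task versus off task, by condition | Section 10 | Condition x two-level Thought |
| Do anxious thoughts predict startle potentiation? | Section 4(d) | None that isolates anxious probes |
| Does faster RT go with larger potentiated startle? | Section 4(d) | None; no RT term |
| Are anxious probes off-task, or excluded? | Not stated | Not stated |

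**The case against.** The plan can be defended on several points.

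- The word Load looks like a slip carried over from Study 2a, and it leaves the arithmetic unchanged. That stands.
- A common conversion (reading C) with a moderate correlation supports 28. That stands too. A reader might infer from the 53% that the sub-study is underpowered or that 28 is a mistake. The documents do not support this, because they nowhere say that 0.4 is the standardized interaction contrast.
- The mismatch with Study 2a does not place an error in Study 2c. Load cells are fixed by design, while thought cells come from participants' reports, so a lower correlation in 2c is plausible, and that is the direction of the implied values. The sources also differ: pilot and published work for 2a, pilot work alone for 2c. On reading C it is 2a that falls short. What remains is a reporting gap across both sub-studies.
- Calling the ANOVA the main analysis does not exclude others, and if anxious probes count as off-task it partly addresses the anxious-thought question. This stands in part: pooled in that way, anxious thoughts are still not separated from other off-task thoughts, and RT is still absent.
- A mixed model is one choice among several. What the gap strictly requires is a named analysis for each question and a coding rule.

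A reader might also infer that the two questions are post hoc. They are not: section 4 states both in advance. Only their analyses are unspecified.

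**Conclusion.** The point holds as a matter of specification and should be fixed. It is certain that the power sentence names a factor absent from the SART and from its planned ANOVA, that no named model isolates anxious thoughts or contains RT, and that the coding of anxious probes is open.

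The power part is weaker. The 28 is under-specified and not shown to be wrong. Power at 28 runs from 41% to 90% over the readings and assumed correlations shown above, with 53% and 82% as the two plainest cases. The conflict with Study 2a holds under any one common scaling of d (49 against 30, or 18 against 28). It disappears if the two sub-studies assume different correlations, which neither states.

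The number of subjects who would drop out of the ANOVA because a thought cell is empty cannot be estimated from the documents.

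**What to change.** 1. In the Study 2c power sentence, replace Load with Thought and restate the power at 28 for that contrast, giving the assumed effect size, correlation and sidedness. If the pilot values are not available, state that 28 subjects give 80% power at two-sided 0.05 for a standardized within-subject interaction contrast of 0.55. Give the matching assumptions for Study 2a so that the two figures can be reconciled. No increase in subjects is asked for.
2. Keep on task versus off task as the main comparison, and fix in advance whether anxious probes count as off-task in it or are left out.
3. Add two analyses labelled secondary, reported as estimates with confidence intervals:
   - a trial-level mixed model of startle on Condition x three-level Thought, giving anxious versus on task and its interaction with Condition; this also keeps subjects with an empty thought cell;
   - a model of startle on Condition x RT, with RT taken from trials before the startle stimulus, and a statement of whether the within-subject or between-subject association is meant.
4. Report how many subjects contribute to each thought category in each condition.

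The cost is protocol wording and some extra analysis, with no new data. The restated power may look less favourable. The added tests are few but likely to have low power, which is why they stay secondary. Subjects with no anxious probes stay in the mixed model but add no within-subject information on that contrast.

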11. HUMAN SUBJECTS PROTECTION

a. Subject selection

i. Both genders will be equally represented. Ethnic representation will reflect the population from which the sample is recruited.

ii. As people get older the probability that they startle decreases. Because startle is our main independent measure it is important to test subjects who are likely to startle in order to collect analyzable data. Based on our experience, we made the decision that 50 would be the upper age limit to ensure usable data and thus justify the minimal risk.

b. Justification for inclusion/ exclusion of children

Children will be excluded because of the aversive nature of the stimuli used in this protocol.

```
CNS IRB Protocol Template (rev. 9-21-11)
```

c. Justification for inclusion of other vulnerable subjects, e.g. cognitively impaired, pregnant, mentally ill

Protections for employees and staff participating in this study include 1) assuring that the participation or refusal to participate will have no effect, either beneficial or adverse, on the subject's employment or position at the NIH, 2) giving employees and staff who are interested in participating the "NIH Information Sheet on Employee Research Participation" prior to obtaining consent, and 3) assuring that there will be no direct solicitation of employees or staff. This study collects sensitive information (e.g. drug and alcohol use, specific medical diagnoses). The PI will train study staff regarding obtaining and handling potentially sensitive and private information about co-workers through staff discussions and written branch/section procedures. Information about sensitive information (e.g. drug and alcohol use, specific medical diagnoses) will be in the participant's NIH medical record.

d. Justification for exclusion of decisionally impaired adults:

All subjects must be able to provide their own consent. We do not want to enroll participants who do not understand the risk/benefit ratio of the study, particularly when there is no benefit to the participants.

e. Justification of sensitive procedures (use of placebo, medication withdrawal, provocative testing)

Not applicable.

f. Safeguards for vulnerable populations

Female participants will undergo urine pregnancy tests prior to experiments. Neither participation nor refusal to participate as a subject will have an effect, either beneficial or adverse, on the participant's employment or position at NIH. The NIH Information Sheet on Employee Research Participation will be available to employees considering enrollment.

12. CONSENT DOCUMENTS AND PROCESS

- a. Designation of those obtaining consent: Study investigators or Associate Investigators identified in the KSP form will obtain informed consent. NIH employees will not be consented by a coworker.
- b. Consent procedures: All participants will receive a verbal explanation in terms suited to their comprehension of the purposes, procedures and potential risks of the study and of their rights as research participants. Participants will have the opportunity to carefully review the written consent form and ask questions regarding this study prior to signing.

Telehealth Consent Procedures: Under certain circumstances, there may be a need to obtain telephone or telehealth consent for this study using NIH-approved platforms. Under these circumstances, the individual will be sent a copy of the consent form. After the document is reviewed, an AI authorized to obtain consent will contact the individual and review the procedures and risks. The participant and the investigator will sign their respective copies, and the former will return their copy to the investigator. One copy each of the signed consent form will be placed in the Medical Record, retained by the investigator, and returned to the participant or parent/guardian. Proper documentation will be made in CRIS.

c. Consent documents There are two consent forms for this protocol, each containing all required elements, and designated as follows: Shock Sural nerve stimulation

13. DATA AND SAFETY MONITORING

- a. Data and Safety monitor: Data and safety monitoring will be conducted by the P.I. who will review the results for each subject.
- b. Data and Safety monitoring plan: All participants are monitored while they are onsite. Paper data are stored in locked cabinets within locked closets/rooms. Electronic data are encrypted and cannot be accessed without obtaining a password. All data are reviewed as they are obtained. The PI will review data and safety parameters at least annually. The PI will document the data and safety review in the research records and at the time of continuing review.

14. STUDY INTERVENTION AND PARTICIPANT DISCONTINUATION/ WITHDRAWAL

14.1 Discontinuation of Study Intervention

Discontinuation from the task will mean discontinuation from the study, and remaining study procedures will be stopped. Only clinical evaluations of AEs and follow up calls may occur following discontinuation. Any new clinically relevant finding will be reported as an adverse event (AE).

Participants are free to withdraw from participation in the study at any time upon request.

An investigator may discontinue or withdraw a participant from the study for the following reasons:

- Completion of study intervention
- If any significant worsening of symptoms or active suicidal ideation, clinical adverse event (AE), laboratory abnormality, or other medical condition or situation occurs such that continued participation in the study would not be in the best interest of the participant
- Concomitant medication use
- Investigator discretion
- Positive pregnancy test

14.2 Participant Discontinuation/Withdrawal from the Study

Participants are free to withdraw from participation in the study at any time upon request.

An investigator may discontinue or withdraw a participant from the study for the following reasons:

- Significant study intervention non-compliance
- If the participant meets an exclusion criterion (either newly developed or not previously recognized) that precludes further study participation
- Subject has completed the study
- Death
- Screen Failure

The reason for participant discontinuation or withdrawal from the study will be recorded in CRIS.

14.3 Lost to Follow-up Not applicable.

15. QUALITY ASSURANCE

a. Monitor

Quality assurance will be monitored by the PI and research team and the NIMH Office of Regulatory Oversight (ORO).

b. Plan

ORO monitors intramural research studies to ensure compliance with GCP, organizational policies and regulations. Audit frequency is determined by the ORO SOP based on the study level of risk. Results of ORO audits are provided to the PI, The Clinical Director and the CNS IRB. This study will undergo audits at least once every three years and for cause.

16. ADVERSE EVENTS AND SERIOUS ADVERSE EVENTS

Definition of Adverse Event

Adverse event means any untoward medical occurrence associated with the use of an intervention in humans, whether or not considered intervention-related (21 CFR 312.32 (a)).

Definition of Serious Adverse Events (SAE)

An adverse event (AE) or suspected adverse reaction is considered "serious" if, in the view of either the investigator or sponsor, it results in any of the following outcomes: death, a life-threatening adverse event, inpatient hospitalization or prolongation of existing hospitalization, a persistent or significant incapacity or substantial disruption of the ability to conduct normal life functions, or a congenital anomaly/birth defect. Important medical events that may not result in death, be life-threatening, or require hospitalization may be considered serious when, based upon appropriate medical judgment, they may jeopardize the participant and may require medical or surgical intervention to prevent one of the outcomes listed in this definition. Examples of such medical events include allergic bronchospasm requiring intensive treatment in an emergency room or at home, blood dyscrasias or convulsions that do not result in inpatient hospitalization, or the development of drug dependency or drug abuse.

Classification of an Adverse Event

Severity of Event

For adverse events (AEs) not included in the protocol defined grading system, the following guidelines will be used to describe severity.

- **Mild** Events require minimal or no treatment and do not interfere with the participant's daily activities.
- **Moderate** Events result in a low level of inconvenience or concern with the therapeutic measures. Moderate events may cause some interference with functioning.
- Severe Events interrupt a participant's usual daily activity and may require systemic drug therapy or other treatment. Severe events are usually potentially life-threatening or incapacitating. Of note, the term "severe" does not necessarily equate to "serious".]

Relationship to Study Intervention

All adverse events (AEs) must have their relationship to study intervention assessed by the investigator who examines and evaluates the participant based on temporal relationship and his/her clinical judgment. The degree of certainty about causality will be graded using the categories below. In a clinical trial, the study product must always be suspect.

- **Related** The AE is known to occur with the study intervention, there is a reasonable possibility that the study intervention caused the AE, or there is a temporal relationship between the study intervention and event. Reasonable possibility means that there is evidence to suggest a causal relationship between the study intervention and the AE.
- Not Related There is not a reasonable possibility that the administration of the study intervention caused the event, there is no temporal relationship between the study intervention and event onset, or an alternate etiology has been established.

Expectedness

The LIP and/or the Medical Associate Investigator will be responsible for determining whether an adverse event (AE) is expected or unexpected. An AE will be considered unexpected if the nature, severity, or frequency of the event is not consistent with the risk information previously described for the study intervention.

Time Period and Frequency for Event Assessment and Follow-Up

The occurrence of an adverse event (AE) or serious adverse event (SAE) may come to the attention of study personnel during study visits and interviews of a study participant presenting for medical care, or upon review by a study monitor.

All AEs including local and systemic reactions not meeting the criteria for SAEs will be captured on the appropriate case report form (CRF). Information to be collected includes event description, time of onset, clinician's assessment of severity, relationship to study product (assessed only by those with the training and authority to make a diagnosis), and time of resolution/stabilization of the event. All AEs occurring while on study must be documented appropriately regardless of relationship. All AEs will be followed to adequate resolution.

Any medical condition that is present at the time that the participant is screened will be considered as baseline and not reported as an AE. However, if the study participant's condition deteriorates at any time during the study, it will be recorded as an AE. Changes in the severity of an AE will be documented to allow an assessment of the duration of the event at each level of severity to be performed. AEs characterized as intermittent require documentation of onset and duration of each episode. At each study visit, the investigator will inquire about the occurrence of AE/SAEs since the last visit. Events will be followed for outcome information until resolution or stabilization.

Adverse Event Reporting

Reportable events for this protocol will be tracked and reported in compliance with Policy 801.

Serious Adverse Event Reporting

Reportable events for this protocol will be tracked and reported in compliance with Policy 801.

Events of Special Interest

Not applicable.

Reporting of Pregnancy

Not applicable.

